## 6. Risk and Benefit Assessment

### 6.1 Risks

No pharmacological intervention or medical procedures will be used in this study. Rather this study aims to develop and test the use of consensus decisional guidance for the medical management of DM in patients with ADRD.

No survey or qualitative interview data will be gathered without patient and caregiver consent (or in some cases, patient assent). However, some questions may cause anxiety, embarrassment or be emotionally upsetting. The RA/RC will receive training in minimizing emotional impact or discomfort and remind subjects that they may discontinue participation at any time. [name] is experienced in qualitative interviews and will also minimize emotional impact or discomfort. In the event of significant emotional upset, the mPIs will be notified and will intervene to address any concerns.

Subject loss of confidentiality is another risk of clinical trials like the one proposed here and with this type of data collection. However, the computerized assisted telephone interview (CATI) and in some cases, in person, data collection method using a REDCap survey tool that we utilize is specifically designed to mitigate such loss as no data is collected with personal identifiers and contact names, addresses and telephone numbers, which are maintained in separate databases.

### 6.2 Protection Against Risks

All study personnel have completed training in Human Subjects Research and HIPPA standards and we have a strong record of quality assurance and maintained confidentiality from prior projects. NYU MCIT and DataCore, the data management experts who will manage the administrative data and the combined database have multiple data security elements in place (see below) and all personnel are trained in Human Subjects Research HIPPA standards, and data security.

To further protect against risk to loss of subject confidentiality, all records will be coded with anonymous identifiers. Only de-identified data will be shared with the research team without a need to know identifying information. Documentation of consent will be encrypted and will not be known by the PM and clinical team. We will keep one separate and password protected and encrypted computer file that contains identifiable data that is necessary to contact subjects (phone numbers and U.S. mailing addresses). This file will be the only file that can link subject names,

addresses, and/or telephone numbers to the study unique codes, and is only accessible by the study Principal Investigators and Research Coordinator.

Qualitative interviews with caregivers and providers/staff will be audio recorded should patients verbally consent. Audio recording is necessary for transcription and qualitative analysis of interviews. Audio tapes of subject interviews will be labeled with subject anonymous identifier (described above), only linked in a secure file accessed only by IRB approved study team. Audio tapes will be destroyed once transcriptions are complete, which will be stored in a HIPAA-compliant NYU secure server.

All other computer files containing data from this study (survey and interview files and files containing medical record and claims data) will be stripped of identifiable data, and subjects will only be differentiated by unique study codes. Data will be compiled from all of the subjects in the study and aggregated for analysis and publication. All identifying data will be eliminated from files before the statistician analyzes the data. All electronic data will be kept in password-protected databases and program files.

Procedures for maintaining confidentiality will be reviewed quarterly with the research team to assure compliance. Audiotaped intervention sessions that will be used to ensure the quality of the intervention and judge treatment fidelity will be reviewed by [name] and subsequently destroyed. A separate consent for audiotaping will be obtained. All study personnel will be trained in data confidentiality, Human Subjects Research and HIPPA compliance, as will the panel managers. Even though the panel managers are part of the clinical team and not the research team, they will interact with the research team and the patient/caregiver dyad and need to understand the context and relationship of the quality improvement program and the research evaluation.

### **6.3 Potential Benefit to Subjects**

We anticipate that participants may receive benefit either from enhanced panel management or usual care and for all we anticipate some immediate benefit regardless of the arm into which they are randomized. All subjects will be recipients of care in clinics that have received guidelines for enhanced care and will be offered referral information for caregiver support services and other informational materials. Contact from an RA may be a break from what for some will be the loneliness of caregiving. We expect some improved caregiver knowledge, decreased sense of burden and improvement in mood for at least intervention subjects. Care recipients may benefit through improved health outcomes. They may also receive increased medical care quality through attention to previously unattended medical issues. Finally, both caregivers and care recipients may receive increased levels of community support through mobilized informal supports and through community agency assistance. This study poses minimal risk to subjects, since the study does not involve tests or treatments beyond that which they would normally receive as part of their normal care. Therefore, the potential benefits outlined above exceed the risks of participation in the study.

For PCPs and staff, participation in interviews poses minimal risk. The opportunity to contribute to better understanding about health service delivery may provide some personal satisfaction and benefit. Information gathered from these interviews may lead to an improved work environment providing direct benefit to participants and colleagues. The interview may also be a place where

PCPs and staff feel free to voice concerns or objections to clinical approaches and this may present a safe space in which to do this.

## 7. Data Analysis

We will begin all analyses with descriptive summary statistics and graphical displays of all variables. Continuous variables will be summarized with means, medians, standard deviation and interquartile range; categorical variables will be summarized with frequencies. We will assess the balance by treatment assignment of patients in the INT and CON clinics with respect to demographic and clinical characteristics (e.g., age, gender, Charlson Index, socioeconomic status, baseline TBQ, etc.) using standard tests (t-tests, Wilcoxon rank-sum tests, and  $\chi^2$  tests as appropriate). Any factors that appear to be unbalanced by treatment assignment will be considered as adjustment factors in the primary analyses. All hypothesis testing will be two-sided and conducted using a significance level of 0.05.

The primary outcome of 'on target' HbA1C values will be measured for each patient as a binary indicator. The primary analysis will use a generalized linear mixed model approach, with a logit link, for the probability of being 'on target.' The treatment group (CON vs INT) will be the primary fixed effect of interest; we will also include the practice as a random effect to accommodate clustering of patients within clinics. We will also explore non-parametric methods such as quantile regression or other rank-based approaches. As noted above, randomization should obviate the need for any additional covariate adjustment, but we will explore whether adjustment for clinic-level characteristics (e.g., clinic size) and provider-level characteristics (e.g., provider demographics and panel size) is necessary. We will use standard assessments of goodness-of-fit, including residual plots, to evaluate the models. Finally, in addition to reporting the treatment difference in terms of the odds ratio from the logistic regression, we will report absolute risk difference as well.

The secondary outcome of TBQ score, transformed into a binary outcome using an appropriate threshold (e.g., the median) will also be assessed using generalized logistic mixed models as described above; the treatment group (CON vs INT) will be the primary fixed effect of interest, with practice included as a random effect. As with the primary outcome, we will assess the need for adjustment using demographic or clinical characteristics, and will evaluate goodness-of-fit using standard approaches. We will also evaluate the TBQ as a continuous score using a linear mixed model. We will assess the validity of the linearity assumption, and seek a suitable transformation of the TBQ score if it appears to be violated. The statistical power for this analysis will be greater than that for the binary version of the outcome because of the additional information provided when using the scale in its original form.

Health care utilization outcomes will be analyzed using similar generalized linear mixed models; indicators of use will employ the logistic link function, and counts of days in various facility types will employ Poisson regression with the log link function. Treatment burden (using the Treatment Burden Scale) and dementia symptoms/cognitive function (using the DSRS) will also be evaluated as important secondary outcomes. We will have repeated assessments of these items at 6, 12, and 24 months, and will apply longitudinal mixed effects models to evaluate the trajectories and assess whether they differ by treatment group. Specifically, we will model time using indicator variables, and include interaction terms between time indicators and treatment group (CON vs INT); the statistical significance of the coefficients of the interaction terms will indicate whether

the trajectories in the outcomes over time differ by treatment group. We will also explore more parsimonious ways of modeling time, for example as a linear or polynomial effect. We will choose link functions that address ordinal outcomes, such as the log link for ordered categorical outcomes, in the context of proportional odds or multinomial logistic regression.

All clinical trials are at risk for missing data. Although we will attempt to retain as high a fraction of participants as possible, we acknowledge that some attrition is likely, leading to missing outcome values. The generalized linear mixed models proposed for the primary and secondary analyses incorporate an assumption of data that are missing at random (MAR), meaning that the likelihood of a value being missing depends on observable characteristics (e.g., sex, age, baseline clinical status, etc). In sensitivity analyses, we will assess the impact of different assumptions about the missing data mechanism, and will determine the robustness of trial results to these different assumptions. These sensitivity analyses will take the several forms. The first extreme value imputation, in which we assume that all members of one intervention group experience either a success or a failure (e.g., HbA1 on or off target) while the opposite occurs in the other intervention group. We will also apply a more formalized assessment using the Index of Sensitivity to Nonignorability, developed by [name] and colleagues, which provides an objective assessment of the robustness of trial results to different assumptions about the missing data mechanism.

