## 1. Purpose of Study and Background

### 1.1 Purpose

The purpose of EQUIPED is to test and evaluate a care quality improvement intervention featuring use of consensus decisional guidance for the medical management of diabetes (DM) patients with Alzheimer's and other forms of dementia (ADRD) in primary care at NYU Langone Health. This quality improvement program will include provider (PCP) workflow enhancements supported by a panel manager (PM) for workflow support, electronic health record (EHR) decision support and feedback, and PCP collaborative learning.

It will test hypotheses about whether care based on explicit standards for DM medical management for people with ADRD will: **H1**) Improve patient symptoms and quality of life while maintaining expected clinical outcomes; **H2**) decrease patient and caregiver management burden and improve care quality based on patient/caregiver preferences; **H3**) (secondary) decrease specialty, ED and hospital utilization.

In order to test and evaluate this program, we will conduct a pragmatic randomized controlled trial (RCT) and evaluate it using mixed methods (surveys and interviews) in 20 NYU Langone Health clinics with the enrollment goal of 500 patients with diagnosed DM and ADRD in the intervention (INT) and control (CON) group (1,000 total).

If EQUIPED demonstrates that patients and family caregivers who receive this quality improvement program achieve established goals for diabetic care in addition to fewer dementia-related symptoms, less caregiver burden and stress, and fewer DM-related adverse events, potentially avoidable and costly utilization may also decrease. This best practice approach could then be widely disseminated to other clinical practices.

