### 1.2 Specific Aims

Specific Aims of the R33 Enhanced Quality In Primary Care for Elders with Diabetes-ADRD (EQUIPED-ADRD) are:

- 1) Implement and evaluate a pragmatic trial in a large healthcare system using cluster randomization, and the practice change framework, that will: manage people with co-occurring DM and ADRD according to the guidelines developed to test our hypotheses and identify additional patients with cognitive impairment and inappropriate DM management.
- 2) Test whether EQUIPED-ADRD will increase the proportion of intervention patients who are in desirable glycemic and blood pressure ranges compared to control patients.
- 3) Test whether the EQUIPED-ADRD intervention will improve dyad perception of care quality and reduce treatment burden.
- 4) Test whether dementia symptoms will deteriorate less in intervention subjects compared to controls.

**Exploratory Aim.** Test whether intervention subjects will use fewer health care services than controls and will have less cognitive decline associated with desired changes in glycemic and blood pressure control.

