## 3. Subject Population

### 3.1 Total Number of Subjects and Sites

We will randomize the **20 largest NYU Langone Health primary care practices**, 9 Intervention (**INT**) clinics and 9 control (**CON**) clinics. We will enroll **1,000** patients (and their caregivers)  $\geq 65$  with diabetes (DM) and Alzheimers disease and other forms of dementia (ADRD) from these practices based on the Inclusion and Exclusion criteria below. As stated in inclusion and exclusion criteria, patients must have a caregiver who will also be enrolled. The patient and caregiver are referred to as a "dyad."

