### **INT Clinics:**

In the INT clinics we will introduce the panel manager (PM) to all clinic staff and develop processes for interaction. The PM will work with INT clinic providers to individualize communication methods between the PCP and PM. Each month INT clinic providers will get a list of eligible patients who have appointments with them in the coming month - those with diagnoses of DM-ADRD and those 75 and older with DM who are out of range for HbA1c or BP. This process gives providers monthly reminders about the ongoing quality improvement study and is a more intensive form of QI intervention than provided to CON clinics.

Because this is a pragmatic trial, the clinical team and a project-funded PM will deliver the intervention, fitting it as closely as possible into usual clinical workflow. The clinical team includes PCPs, occasional APNs and PAs (who function as PCPs), RN's, MA's, office staff, and clinic onsite administration. The PM will be part of the team; PMs providing chronic disease self-management support (usually telephonic) are clinic team members in many healthcare systems.

We will assign two PMs to 9 randomly selected INT clinics. Each PM will have 4.5 INT clinics and will engage and focus on their first clinics in a randomly ordered step-wise fashion working within 1-2 clinics over a focused 3-month period before moving on to the next 1-2 clinics for 3 months, then the last 1-2 clinics for 3 months. Our preliminary data suggests 20-50 patients per INT clinic with DM-ADRD  $\geq 65$  years; and about an equal number with DM without ADRD who will screen positive for cognitive impairment, most of whom are  $\geq 75$  years and identified by HbA1c/BP over or under treatment, or identified by provider referral, which we will allow. With 9 INT clinics, given our preliminary data about patient numbers, each PM will have an anticipated 300 dyads. PMs can engage about 33 patients/month, making initial 300 patient/CG contact in 9 months.

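### Baseline balance is tested with patient-level t, Wilcoxon and chi-square tests although clinics are randomised, so the p-values ignore clustering and could misdirect the choice of adjustment covariates

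*Combined protocol and SAP*

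**What the plan says.** The first specific aim (Section 1.2) is to "Implement and evaluate a pragmatic trial in a large healthcare system using cluster randomization". Section 3.1 randomises the "20 largest NYU Langone Health primary care practices" but in the same sentence splits them into 9 intervention and 9 control clinics. Section 4, under INT Clinics, also has 9: "We will assign two PMs to 9 randomly selected INT clinics". Section 1.1 gives an "enrollment goal of 500 patients with diagnosed DM and ADRD in the intervention (INT) and control (CON) group (1,000 total").

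Section 7 then states: "We will assess the balance by treatment assignment of patients in the INT and CON clinics", naming age, gender, Charlson Index, socioeconomic status and baseline TBQ as examples, and doing so "using standard tests (t-tests, Wilcoxon rank-sum tests, and" chi-square tests. The next sentence gives the result a use: "Any factors that appear to be unbalanced by treatment assignment will be considered as adjustment factors in the primary analyses". All hypothesis testing is two-sided at 0.05. The practice random effect appears in the following paragraph, for the outcome model only. That paragraph also says that randomisation should make further covariate adjustment unnecessary.

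**The concern.** The t-test, the Wilcoxon rank-sum test and the chi-square test all assume independent patients. Here whole clinics are allocated, and patients in one clinic tend to resemble each other in age, socioeconomic status and similar characteristics. The difference between arms then carries between-clinic variance that these tests leave out of the standard error. The plan accepts this for the HbA1c outcome but not for the baseline variables.

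Two things are at stake. First, the tests have a consequence: factors that look unbalanced become candidates for adjustment in the primary analysis, so a mis-sized test could steer the choice of covariates. Second, a reader of the baseline table may use its p-values to judge whether recruitment differed by arm. That is a natural question here: the consent steps in Section 5.2.1 list the introductory letter under INT only, and Section 4 refreshes the sample in both arms during the study. A test that rejects too often cannot separate differential recruitment from ordinary variation between clinics.

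**Working it through.** The plan states no ICC, design effect, power calculation or false-flag rate, so there is no figure of its own to reproduce.

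**Inputs from the documents.** 1,000 patients, 500 per arm (Section 1.1). Clinic count 20 (Sections 1.1 and 3.1) or 9 + 9 = 18 (Sections 3.1 and 4). Mean cluster size m = 1,000/20 = 50 or 1,000/18 = 55.6. Two-sided level 0.05 (Section 7).

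**Assumptions, not in the documents.** ICC of a baseline variable from 0.005 to 0.10; equal cluster sizes, then a coefficient of variation (CV) of cluster size of 0.4.

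**Formulae.** Design effect DE = 1 + ((1 + CV²)m − 1) × ICC. If a variable is balanced in expectation, a patient-level test at 5% flags it with probability 2[1 − Φ(1.96/√DE)].

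Worked example, m = 50, ICC 0.02, equal clusters: DE = 1 + 49 × 0.02 = 1.98; 1.96/√1.98 = 1.39; probability 16.4%.

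| ICC | DE, m = 50 | Flagged | DE, m = 55.6 | Flagged |
|---|---|---|---|---|
| 0 | 1.00 | 5.0% | 1.00 | 5.0% |
| 0.005 | 1.25 | 7.9% | 1.27 | 8.2% |
| 0.01 | 1.49 | 10.8% | 1.55 | 11.5% |
| 0.02 | 1.98 | 16.4% | 2.09 | 17.5% |
| 0.05 | 3.45 | 29.1% | 3.73 | 31.0% |
| 0.10 | 5.90 | 42.0% | 6.46 | 44.0% |

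**Simulation check** (equal clusters, no true difference; 20,000 runs for the t-tests, 4,000 for the others). The ICCs are 0.01, 0.02, 0.05 and 0.10 in that order.
- t-test: 10.7%, 16.5%, 29.3%, 42.1% with 20 clinics of 50; 11.3%, 17.3%, 31.3%, 44.7% with 18 clinics of 56.
- Wilcoxon: within about one percentage point of the t-test.
- Chi-square on a variable split at its median, 20 clinics of 50: 9.0%, 13.6%, 23.4%, 34.9%.
- t-test on clinic means (16 or 18 degrees of freedom): 4.7% to 5.4% at every ICC from 0 to 0.10.

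**Sensitivity** (formula, same four ICCs).
- Smaller clusters lower the rates: m = 35 gives 9.0%, 13.0%, 23.3%, 35.0%; m = 20 gives 7.2%, 9.5%, 16.0%, 25.0%. These sizes matter because of Section 4: "Our preliminary data suggests 20-50 patients per INT clinic with DM-ADRD", with about as many again expected to screen positive.
- Unequal clusters raise them slightly: CV 0.4 gives 11.8%, 18.0%, 31.8%, 44.9% at m = 50, and 12.5%, 19.3%, 33.7%, 47.0% at m = 55.6.

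**The case against.** The strongest reply is that nothing in the primary inference depends on these tests. Flagged factors are only to be considered for adjustment, no p-value cut-off for entry is set, and the same section expects randomisation to make adjustment unnecessary. The treatment effect is tested in a model with a practice random effect. This stands. A reader might infer that every flagged variable enters the HbA1c model, or that the trial's type I error is inflated; the documents support neither. Even under automatic entry of every flagged covariate, a simulation of a clinic-level treatment test gave type I error of about 3% to 4%, below the nominal 5%. It assumed 10 covariates with coefficient 0.15 each, a linear outcome and an outcome ICC of 0.03.

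The size also rests on assumption. One might want to quote a single false-flag rate for this trial, but without an ICC, a cluster-size distribution or a settled clinic count, only a conditional range is justified. A rate near 47% at ICC 0.10 needs unequal clusters as well.

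A flagged variable is not necessarily a false alarm in the sample: a chance difference between clinics is a real difference between the arms as enrolled, and may be a sensible reason to adjust. The right description of the null case is balance in expectation. Nor do the documents call the baseline table the main check for recruitment bias; that is a use a reader may make of it.

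Finally, the plan says the tests are applied as appropriate. This reads most naturally as choosing a test by type of variable. It does not state an allowance for clustering.

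What remains is that the named tests have the wrong error rate under clinic randomisation, and that their results inform the choice of covariates.

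**Conclusion.** The point holds as a unit-of-analysis error in the balance assessment. With equal clusters of about 50 to 56 patients, the t-test flags a variable balanced in expectation about 8% of the time at ICC 0.005, 10-12% at 0.01, 16-18% at 0.02, 29-31% at 0.05 and 42-45% at 0.10, against a nominal 5%. For 10 such variables (an assumed number), that is about 1.1 to 4.4 expected flags for ICC 0.01 to 0.10 (10 × 0.108 to 10 × 0.440), instead of 0.5. The ICCs and equal sizes are assumptions; smaller clusters or dichotomised variables give less, and unequal clusters slightly more. The direction holds for any ICC above 0 and does not depend on whether 18 or 20 clinics is right, although the documents must reconcile that count before one design effect can be quoted.

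The harm is limited to two things: possible misdirection of covariate choice in the primary HbA1c analysis, and a baseline table that may suggest imbalance or differential recruitment where there is only between-clinic variation. The validity of the treatment test is not in question on this ground. The change should be made because the error is plain and cheap to correct.

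**What to change.** Amend Section 7 as follows.

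- Remove the patient-level significance tests of baseline balance and report standardised differences by arm.
- If a test is wanted, for example to look for differential recruitment, run it on clinic means or in a model with a clinic random effect and (clinics − 2) degrees of freedom: 16 for 18 clinics, 18 for 20.
- State that no patient-level p-value decides adjustment in the primary model.
- Reconcile the count of 20 clinics with 9 + 9 in Sections 1.1, 3.1 and 4, since the degrees of freedom depend on it.

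The cost is wording in the analysis plan. No data collection changes. Standardised differences are a reporting convention; the essential correction is that any p-value reported for balance should respect the clinic.

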Consistent PCP care	EHR	% Visits by PCP versus other ambulatory providers	Pt	X	X	X	X

New home health aide or increased hours	Survey	Yes/no; HHA resource changes	Pt	X	X	X	X
New home health care services	Survey	Yes/no	Pt	X	X	X	X
Insurance	EHR	Categorical: Yes/No, Medicare, Medicaid, HMO	Pt	X	X	X	X
DM-ADRD-Specific							
Has a caregiver (Defined: Sec. B5)	EHR	Yes/No	Pt	X	X	X	X
Caregiver living arrangement	Survey	Categorical: Live with subject, close proximity (miles), other	CG	X	X	X	X
Clinic-Specific							
Clinic Size	Admin	Number primary care providers / number of patients	Clinic	X			X
Clinic Support	Admin	Number of clinic support staff / provider	Clinic	X			X
Proportion Medicare/Medicaid	Admin	Insurance data specific to Medicare/Medicaid categories	Clinic	X			X
EQUIPED Process of Care Measures							
Provider use of structured template	EHR	Counts: visit note/templates; proportion of visits with templates	PCP		X	X	X

Provider educational attendance	Admin	Proportion (n, %) of educational sessions attended	PCP		X		
PM – PCP Communication	EHR	Counts: emails, forwarded notes between PM and PCP	PM/PCP		X	X	X
Change in diabetic medication	EHR	Counts: change (add, delete); dosing (increase, decrease)	Pt	X	X	X	X
Change in antihypertensive medication	EHR	Counts: change (add, delete); dosing (increase, decrease)	Pt	X	X	X	X
Medication complexity	EHR	Sum of unique medications, daily dosing frequency/differences	Pt	X	X	X	X
Anticholinergic medication burden	EHR	Anticholinergic medication burden scale	Pt	X	X	X	X
PM – CG contact frequency	EHR	Counts: CG visits with PM (by type: email, phone, in-person)	CG		X	X	X
Referrals for CG-support services	EHR	Proportion (n, %) of CGs referred to programs / receipt of service	CG		X	X	X
Cognitive screening of eligible patients	EHR	Proportion (n, %) of DM-eligible patients screened w/ MiniCog TM39	Pt		X	X	X
Outcome Measures							
General							
Hemoglobin A1C Change	EHR	Proportional change: patients with in-range values versus not	Pt	X	X	X	X

Blood pressure change	EHR	Proportional change: patients with in-range values versus not	Pt	X	X	X	X
Treatment Burden Questionnaire	Survey	15-item survey modified for CG administration (0-10 likert) 	Pt	X	X	X	X
Non-acute care use	ResDAC	Counts: provider ambulatory visits / all health system contacts	Pt	X	X	X	X
Acute care use**	ResDAC	Counts: ED, hospital / #bed days	Pt	X	X	X	X

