We will also measure structure of care variables. These include patient use of consistent PCP care, home health services, and patient insurance. Clinic characteristics are size, support staff number, proportion of Medicare and Medicaid patients. Several baseline variables relate to diabetes but because they are also outcome variables they will be described later. As shown in table 1, many of these baseline and control variables are measured in the EHR and Epic administrative reports, or by claims. Some are measured by validated survey instruments, which are discussed briefly below.

We will collect many process of care measures at baseline and at follow-up. These include: a) provider use of Epic templates and tools; b) provider attendance at educational sessions; c) PM-PCP communication; d) PM-caregiver contact frequency; e) referral for caregiver-support services; f) cognitive screening of diabetes patients over 75; g) change in diabetes medications; h) change in hypertensive medications; i) change in anticholinergic burden; j) change in medication complexity. These variables are measured by EHR review and Epic administrative systems.

Outcome variables include HbA1c level and blood pressure. These variables will be measured at 0, 6, 12 and 24 months when available. Our main outcome is the proportion of patients achieving consensus HbA1c targets. BP will be measured by proportion of patients achieving consensus BP targets per our guideline. These variables will be measured by the EHR.

Utilization outcome variables are ED, hospital, SNF and ambulatory clinic utilization measured by EHR and by claims (for non-New York Langone Health utilization). SNF days must be measured by claims; Epic reports have discharge destination but do not have SNF days. Utilization variables will be measured at 6, 12, 24 months; the baseline measures include a 20 month look back at utilization.

Multiple caregiver reported outcomes about the caregiver and about the patients will also be

collected at 0, 6, 12, 24 months. General outcomes include: a) caregiver perception of care quality (our main caregiver-reported outcome), dyad care goals, preferences, and satisfaction; b) treatment burden; c) caregiver global health. Dementia and diabetes specific outcomes include: a) patient dementia symptoms; b) caregiver diabetes stress.

Below is a brief description of the instruments we will use, all of which have been studied and validated, although not always with caregivers.

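### The primary model does not fix baseline HbA1c status in advance; leaving patient-level adjustment to a look at the data gives up some power, though the test stays valid

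*Combined protocol and SAP*

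**What the plan says.** Section 7 (Data Analysis) defines the primary outcome as one binary on-target indicator per patient. On the model it says: "The treatment group (CON vs INT) will be the primary fixed effect of interest; we will also include the practice as a random effect". Its stated default is that "randomization should obviate the need for any additional covariate adjustment", with clinic-level and provider-level characteristics to be explored.

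Patient-level covariates enter by a different route. Patients in the two arms are compared by t, rank-sum and chi-square tests on a list of examples ("e.g., age, gender, Charlson Index, socioeconomic status, baseline TBQ, etc"), and then: "Any factors that appear to be unbalanced by treatment assignment will be considered as adjustment factors in the primary analyses". No cutoff is given. The paragraph on the secondary outcome adds: "As with the primary outcome, we will assess the need for adjustment using demographic or clinical characteristics". That sentence has no imbalance condition, but it fixes nothing in advance either.

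Baseline HbA1c is planned. Table 1 marks the HbA1c row at baseline, and the Measures text says of HbA1c and blood pressure: "These variables will be measured at 0, 6, 12 and 24 months when available". The balance examples include the baseline of a secondary outcome (TBQ). They do not name HbA1c, although the list is open-ended.

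**The concern.** A patient's HbA1c status at baseline is a natural predictor of the same status at follow-up. Adjusting for it narrows the confidence interval of the risk difference and raises power, but the gain comes on average over all trials only if the covariate is in the model whatever the observed balance. If it enters only when an imbalance is noticed, most trials are analysed without it. With nine clinics per arm there is little precision to spare.

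Section 7 can also be read as supporting either an unadjusted or an adjusted primary analysis, with the choice made after the data have been seen.

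**Working it through.** **Inputs from the documents.** 1,000 patients (Section 1.1); 9 INT and 9 CON clinics (Section 3.1, which also speaks of 20 practices; 18 is used here); two-sided 0.05 (Section 7). Mean clinic size m = 1000/18 = 55.6.

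**Assumed, because the documents give none.** 50% on target in CON (variance 0.25, used in both arms); true effect 12 percentage points; ICC 0.01 to 0.05; patient-level and clinic-level correlations rw and rc between baseline and follow-up status. The plan states no power, so there is no figure to reproduce.

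**1. Variance factor from one pre-specified patient-level slope (risk-difference scale).**

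F = [ICC·m·(1 − 2·rw·rc + rw²) + (1 − ICC)(1 − rw²)] / [ICC·m + 1 − ICC]

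At ICC 0.02, ICC·m = 1.111 and the denominator is 2.091. For rw = 0.4, rc = 0.6: (1.111 × 0.68 + 0.98 × 0.84)/2.091 = 0.755.

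**2. Power.** SE = √(2 × 0.25 × [ICC + (1 − ICC)/m] × F / 9), with a noncentral t on 16 df. Unadjusted at ICC 0.02: √(2 × 0.25 × 0.03764/9) = 0.0457, noncentrality 0.12/0.0457 = 2.62.

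| rw, rc (ICC 0.02) | F | SE | Power |
|---|---|---|---|
| unadjusted | 1 | 0.0457 | 69% |
| 0.25, 0.25 | 0.938 | 0.0443 | 72% |
| 0.4, 0.4 | 0.840 | 0.0419 | 77% |
| 0.4, 0.6 | 0.755 | 0.0397 | 81% |

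For 0.4, 0.6 the rise is from 82% to 90% at ICC 0.01 and from 46% to 59% at ICC 0.05. This is a t test on clinic means, standing in for the planned mixed model.

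**3. What an imbalance trigger recovers.** A patient-level test that ignores clustering flags baseline status by chance with probability 2·P(Z > 1.96/√DE), where DE = 1 + (m − 1)·ICC = 1.55 / 2.09 / 3.73 at ICC 0.01 / 0.02 / 0.05. The result is 11% / 18% / 31% (11% / 16% / 29% with 20 clinics). Simulated power at ICC 0.02 (4,000 trials per setting, Monte Carlo error about 1.5 points), for unadjusted / adjust if p<0.05 / pre-specified: 69/70/73% at 0.25, 0.25 and 69/72/81% at 0.4, 0.6. The p<0.05 cutoff is one version of a rule that the plan leaves open.

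**4. Type I error.** Simulated null rejection was 4.8–5.3% unadjusted, 3.5–4.9% with the trigger and 4.8–5.6% pre-specified.

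**5. Which correlations are plausible.** Sections 1.3 and 4 treat both high and low HbA1c as a problem, so the target is taken as a two-sided range; its limits are not in these documents. For a normal HbA1c with baseline to follow-up correlation 0.7 and ranges 0.8 to 1.5 SD wide (all assumed), the correlation of in-range status is about 0.15 to 0.38. If the range is centred on the mean, a linear HbA1c term has zero correlation with in-range status; it becomes informative only as the range moves off centre.

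**6. Logit scale.** In simulated unclustered fits (500 per arm, 50% v 58%, latent correlation 0.7), adjustment moved the log odds ratio from 0.320 (SE 0.127) to 0.423 (SE 0.147), and power from 71.5% to 83.8%. The SE rises, but the estimate rises more.

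**7. Cost of dropping patients without a baseline value.** Variance inflation = [ICC + (1 − ICC)/(m(1 − d))] / [ICC + (1 − ICC)/m]. At ICC 0.02 this is 1.05 for d = 10% and 1.12 for d = 20%. Multiplied by 0.938, the net factor is 0.985 or 1.05, so the gain at correlation 0.25 disappears.

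**The case against.** Randomisation already protects the unadjusted comparison, and a pragmatic trial may prefer a simple model. That is fair as to validity, and step 4 agrees, but it does not answer the loss of power.

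Baseline may in effect be used already: Table 1 describes the HbA1c outcome as "Proportional change: patients with in-range values versus not" with a baseline column, and the list of balance factors is open. Repeated measures are therefore not ruled out. But Section 7 describes one indicator per patient for HbA1c, with no time term, and sets out its longitudinal models for the repeated secondary measures, such as treatment burden and DSRS. The ambiguity shows that the analysis is not fixed; it does not show that baseline is in it.

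The gain may be small. This stands. At a status correlation of 0.25 it is about 3 points of power, and dropping patients without a baseline value could cancel it. It also stands that imbalance is not the sole stated route to adjustment, since the need for it will be assessed more generally, and that precision in the ordinary sense improves on the risk difference, not on the log odds ratio.

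A reader might further infer that the unadjusted estimate is biased because follow-up HbA1c will be missing differently by arm. The documents state no such pattern. Section 7 gives baseline clinical status only as an example in its definition of missing at random, and it already plans extreme-value imputation and a formal nonignorability index.

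**Conclusion.** The point holds as one of efficiency and of fixing the analysis in advance. Baseline HbA1c status is due to be collected, is not in the stated primary model, and could enter only through a discretionary decision that recovers little of the available gain.

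Under the assumptions above (18 clinics, about 1,000 patients, 12-point effect, ICC 0.02), pre-specification raises power from about 69% to between 72% and 81%. The lower part is more plausible for a two-sided target. Confidence is high that pre-specification is the better rule and only moderate on the size.

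A reader might infer that the primary test is invalid or its type I error inflated. The checks do not support this. The balance tests ignore clustering, which makes them uninformative, but that is not what costs power. Nor do the documents support larger claims of gain, which would need a status correlation near 0.5 or above. The change is worth making before outcome data are seen; it is not a reason to doubt the design.

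**What to change.** In Section 7, replace the imbalance-triggered rule with pre-specified adjustment, whatever the observed balance:

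- **Covariates:** baseline HbA1c category (below, in or above target, or on target yes/no), not a linear HbA1c term, plus a short fixed list such as age, sex and Charlson index.
- **Baseline window:** the last value before the clinic's intervention start or, for later entrants, before enrolment and first panel-manager contact. Use the same look-back length in both arms. INT clinics start in steps, so each CON clinic needs an equivalent reference date set in advance.
- **Missing baseline:** keep these patients, by multiple imputation or a missing category.
- **Reporting:** give the standardised risk difference, note that the odds ratio is conditional, and keep the unadjusted model as a sensitivity analysis.

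Do not add the clinic mean of baseline. With 18 clinics, estimating the extra slope raised the simulated variance factor in five of six settings (for 0.4, 0.6: 0.79 to 0.83, 0.73 to 0.78 and 0.71 to 0.75 at ICC 0.01, 0.02 and 0.05).

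The cost is SAP wording and slightly more analysis work, on variables already planned. There is a small attenuation if some INT baselines are measured after the intervention has begun: with an assumed slope of 0.4 and a 5-point shift in 20% to 40% of INT patients, 0.4 × 5 × 0.2 to 0.4 = 0.4 to 0.8 points of the effect.
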